The analyses for Hypothesis 2.2 address the question of whether the individual (self-efficacy, spiritual well-being), interpersonal (social support), and neighborhood factors (cessation resources) explain (mediate) the relationship between the outcome (6- and 12-month cessation) and the intervention (Sister-to-Sister). In mediator analyses, it is posited that variation in a given independent variable (intervention) accounts for variation in the mediators (self-efficacy, spiritual well-being, social support, cessation resources) and variations in mediators account for variations in outcome (6-and 12-month cessation). For these analyses, we will follow the methods of Baron and Kenney [149], Holmbeck [150], and Kraemer [151]. GLMM analyses as outlined above will evaluate the relationship between the outcome (6- and 12-month cessation) and the intervention (Aim 1). Next, the relationship between intervention and the putative mediator variables (self-efficacy, spiritual well-being, social support, cessation resources) will be evaluated as described for Hypothesis 2.1. Finally, the mediating effect of self-efficacy, spiritual well-being, social support, cessation resources on a significant treatment effect will be evaluated in a GLMM model that simultaneously regresses treatment (TX vs C) and the putative mediating variables on outcome (smoking cessation). A significant smoking cessation/treatment relationship that becomes nonsignificant following the addition of the putative mediator covariable suggests that the latter accounts for (mediates) the former observed relationship. For example, we conclude that the relationship between treatment and smoking cessation is mediated by self efficacy if the variable representing self efficacy is significant and a previously significant treatment effect becomes nonsignificant in the multivariable model containing both.

102,10:1513-1684.

144. Little RJA, Rubin DB (1987) *Statistical Analysis with Missing Data*. 1987. J. Wiley & Sons, New York.

145. Little RJA, Rubin DB (1987) *Statistical Analysis with Missing Data*. 1987. J. Wiley & Sons, New York.

146. Gibbons R. *Longitudinal Data Analysis*. 2006. John Wiley and Sons, Inc. New York.

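### The Hypothesis 2.2 mediation rule leaves open whether factors are judged together or singly, and its conclusion does not require treatment to have moved the factor it credits

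*SAP*

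**What the plan says.** The mediator analysis in the SAP (Analyses for Secondary Aims, Hypothesis 2.2) has three steps.

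1. Treatment is related to cessation, as in Aim 1.
2. Treatment is related to each factor, as for Hypothesis 2.1: "Next, the relationship between intervention and the putative mediator variables" is to be evaluated.
3. A final GLMM "simultaneously regresses treatment (TX vs C) and the putative mediating variables on outcome". The same sentence lists four factors: self-efficacy, spiritual well-being, social support and cessation resources.

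The next sentence moves to the singular. A treatment effect that "becomes nonsignificant following the addition of the putative mediator covariable suggests that the latter accounts for (mediates) the former observed relationship".

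The worked example then gives the rule for concluding mediation. On the factor, it says that the relationship "is mediated by self efficacy if the variable representing self efficacy is significant". On treatment, it asks that an effect found earlier is one that "becomes nonsignificant in the multivariable model containing both".

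The rule therefore has two conditions: the factor is significant, and treatment loses significance. No indirect effect, and no interval for one, is specified.

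**The concern.** Two things are left loose in one paragraph.

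**Which model decides.** The plural in step 3 points to one model with all four factors. The singular covariable and the word for two items in the example point to treatment plus one factor. Two careful analysts could fit different models, and the choice could be made after the results are seen.

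**What the conclusion requires.** Step 2 is carried out, but its result is not among the conditions for concluding mediation.

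The two readings fail in different ways.

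- *Factors together.* Losing the treatment effect is a property of the whole set. The rule still credits any factor that is itself significant, including one that treatment did not move.
- *Factors singly.* A factor that treatment moves, but that does nothing for quitting, can be credited because it correlates with the factor that works. Requiring step 2 does not help, because this factor passes it.

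At stake is whether a factor named under Aim 2 as a mediator is one.

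**Working it through.** **No plan figure to reproduce.** The SAP states no sample size, quit rate or significance level for this analysis. Everything numerical below is assumed, apart from two-sided 0.05, which is inferred from the SAP's use of 95% CIs.

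**Set-up.** Two factors suffice. M1 is the true mediator and M2 the factor that should not be named.

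- M1 = 0.6·T + e1 and M2 = a2·T + e2, with unit-variance errors and correlation r.
- logit P(quit) = −2.2 + c·T + 0.9·M1 + b2·M2, where c is the direct treatment effect.
- 420 women, no clustering, results among trials with a significant total treatment effect.
- SAP rule: name M2 if its coefficient is significant and treatment, significant alone, is no longer significant.

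First case: M2 predicts quitting but is not moved (a2 = 0, b2 = 0.5, r = 0.3). Second case: M2 is moved but inert (a2 = 0.5, b2 = 0, r = 0.3 to 0.5).

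**Why the joint reading fails in the first case (c = 0).** In the joint model the treatment coefficient is 0 and that of M2 is 0.5, so both conditions tend to be met. Yet the indirect effect through M2 is 0 × 0.5 = 0; all of it runs through M1, 0.6 × 0.9 = 0.54.

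**Why the one-factor reading fails in the second case (c = 0).** Given T and M2, the mean of M1 is (0.6 − 0.5r)·T + r·M2. Leaving M1 out therefore gives, approximately on the log-odds scale:

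- coefficient of M2: 0.9r, which is 0.27 at r = 0.3 and 0.45 at r = 0.5, though its true effect is 0;
- coefficient of treatment: 0.9·(0.6 − 0.5r), which is 0.405 and 0.315, down from 0.54.

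The inert factor looks active and the treatment effect shrinks.

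**Simulated false naming of M2**

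| Case and reading | c = 0 | c = 0.8 | With the correction |
|---|---|---|---|
| First case, factors together | about 88% | 15% | 5% or less if treatment must also significantly move M2 |
| Second case, one factor at a time | 26–53% | 1–2% | 6% or less in the joint model; requiring step 2 changes nothing |

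**Sensitivity.**

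- True mediator moved 0.8 SD, log-odds 0.8 per SD, c = 0, 200 to 800 women. First case, joint: 72–97%, or 3–5% with the step 2 condition. First case, one factor at a time: 1–11%. Second case (M2 moved 0.6 SD, r = 0.5), one factor at a time: 34–47%, against about 5% jointly. The two models disagreed about M2 in 66–96% of runs in the first case and 35–48% in the second.
- 420 women as above, but uncorrelated factors in the first case, joint: 74% with b2 = 0.4 and 95% with b2 = 0.7. Keeping b2 = 0.7, a direct effect of 0.4 gives 66% and 0.8 gives 17%. Second case, one factor at a time: 27% (r = 0.3) and 54% (r = 0.5), falling to 3% and 8% with a direct effect of 0.6.

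**Conditioning.** With 420 women and c = 0, only about 42–44% of simulated trials had a significant total effect. Over all trials the rates are therefore about 0.42 × 88% = 37% to 0.44 × 88% = 39% in the first case, and 0.42 × 26% = 11% to 0.44 × 53% = 23% in the second.

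**The case against.** The strongest defence is that the paragraph is sequential and should be read whole. It starts from the premise that the intervention accounts for variation in the mediators, tests that in step 2, and only then fits the final model. Hypothesis 2.2 itself speaks of positive changes in the factors, and established mediation methods are cited. An analyst who named a factor that treatment had not changed would be going against all of this.

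Much of that stands, and it rules out several stronger readings.

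- A reader might infer that the SAP judges each factor in a model holding nothing but that factor and treatment. It does not say so: a joint model also contains treatment and self-efficacy. The text is ambiguous between two models; it does not prescribe both.
- A reader might infer that the treatment-to-factor test is missing. It is planned. It is absent only from the conditions for concluding mediation.
- A reader might add the two failures together. They belong to different readings, and under the one-factor reading an unmoved factor is seldom named (1–11%).
- A reader might take the percentages as this trial's error rate. They rest wholly on assumed inputs and are highest when a single factor carries the entire effect.
- A reader might say that Aim 2 undertakes to identify which level carries the effect. Its wording is only to determine whether these factors mediate.

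The defence does not close the point. Step 2 says the relation will be evaluated, and the premise is posited; the explicit concluding sentence uses neither. Even with step 2 enforced, the one-factor reading still credits the moved but inert factor.

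**Conclusion.** The concern holds in a limited form. The deciding model is not fixed, and the stated conclusion does not depend on the planned treatment-to-factor result. Either reading can name a factor that is not a mediator, by different routes.

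The size is illustrative: about 88% falling to 15% under the joint reading, and 26–53% falling to 1–2% under the one-factor reading, as the direct treatment effect goes from none to 0.8 log-odds. The direction is the same under every set of inputs tried with no direct effect; the size is not. The figures assume 420 women, two factors, no clustering and a significant total effect.

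This affects a secondary aim and leaves the Aim 1 analysis untouched. It should be corrected because the rule decides what is concluded about mechanism.

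**What to change.** In the Hypothesis 2.2 paragraph of the SAP:

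1. State that the deciding model contains treatment and all four factors, with the neighborhood and pair terms already planned.
2. Replace the loss-of-significance rule by one rule. For each factor, combine its treatment effect from Hypothesis 2.1 with its coefficient in the joint model to give its specific indirect effect, and report a 95% CI. Credit the factor only if that interval excludes zero. Name in advance the method used for the interval.
3. Keep one-factor models as descriptive, and reword the self-efficacy example to match.

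This answers both failures. A factor that treatment does not move, or that has no coefficient of its own in the joint model, has a specific indirect effect of zero.

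The cost is SAP wording plus an interval computed from models already planned. The drawbacks are somewhat wider intervals when factors are correlated, and that chains in which one factor acts through another will not be shown.
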